#### Table 1: SAP Amendments

SAP version number	Date Approved	Protocol version number <del>†</del>	Section number changed	Description of and reason for change	Timing of change with respect to interim/final analysis	Blind Reviewer
				SAP moved to the current BCTU SAP Template.		Name: [name] Signature: [name] Date: 23/02/2022
2.0 22/02/2022 9.0	9.0	version	Update to definition of adherence to include women who do not receive an initial MTX injection or their allocated intervention as a result of a clinical change in condition (clinical change requiring immediate surgery post-randomisation) to be considered adherent.	Prior to database lock for final analysis	Name: [name] Signature: [name] Date: 23/02/2022	
	template)	Update to analysis population to exclude any women who are randomised and consent was not obtained.		Name: [name] Signature: [name] Date: 23/02/2022		
				An additional sensitivity analysis added for the primary outcome to exclude women who are found to violate the inclusion/exclusion criteria post- randomisation.		Name: [name] Signature: [name] Date: 23/02/2022

SAP version number	Date Approved	Protocol version number <del>†</del>	Section number changed	Description of and reason for change	Timing of change with respect to interim/final analysis	Blind Reviewer
				Update to adjustment covariates. Version 1.0 of the SAP included hCG (log transformed) and BMI as adjustment factors in their continuous form. Log transformation of hCG was considered to account for the fact it is a skewed variable. We propose adjusting for hCG in its categorised form (as per minimisation categories) to account for this. BMI will also be included in its categorised form for continuity in adjustment of analysis models in line with subgroup analyses. Centre will be considered a fixed effect for time to event outcomes.		Name: [name] Signature: [name] Date: 23/02/2022
				Sensitivity analysis using imputation methods removed and alternative approach for sensitivity analysis for missing data included (tipping point analysis for each treatment group). hCG level considered a key subgroup variable, BMI and ectopic size considered exploratory subgroup variables. For all subgroup analyses a ratio of the treatment effect within subgroups will also be provided.		Name: [name] Signature: [name] Date: 23/02/2022 Name: [name] Signature: [name] Date: 23/02/2022

SAP version number	Date Approved	Protocol version number <del>†</del>	Section number changed	Description of and reason for change	Timing of change with respect to interim/final analysis	Blind Reviewer
				P-values presented for the primary outcome only (removed from secondary outcomes), in line with current statistical practice.		Name: [name] Signature: [name] Date: 23/02/2022
				An additional sensitivity analysis added for the secondary outcome (time to hCG resolution) to change the threshold of resolution to $\leq$ 30 IU/L (from $\leq$ 15 IU/L) to account for the fact some sites do not follow-up women to a hCG $\leq$ 15 IU/L as standard care.		Name: [name] Signature: [name] Date: 23/02/2022

†This SAP was written based on information contained in the trial protocol version as listed here.

Abbreviations & Definitions					
Abbreviation / Acronym	Meaning				
AE	Adverse Event				
BCTU	Birmingham Clinical Trials Unit				
BMI	Body Mass Index				
CI	Confidence Interval				
CONSORT	Consolidated Standards of Reporting Trials				
CRF	Case Report Form				
DMC	Data Monitoring and Ethics Committee				
EP	Ectopic Pregnancy				
ISRCTN	International Standard Randomised Controlled Trial				
	Number				
ITT	Intention to Treat				
MNAR	Missing Not at Random				
MTX	Methotrexate				
NHS	National Health Service				
RCT	Randomised Controlled Trial				
RD	Risk Difference				
RR	Risk Ratio				
SAE	Serious Adverse Event				
SAP	Statistical Analysis Plan				
SUSAR	Suspected Unexpected Serious Adverse Reaction				
TSC	Trial Steering Committee				
UK	United Kingdom				
Term	Definition				
International Standard Randomised Controlled Trial Number	A clinical trial registry				
Protocol	Document that details the rationale, objectives, design, methodology and statistical considerations of the study				
Randomisation	The process of assigning trial subjects to intervention or control groups using an element of chance to determine the assignments in order to reduce bias.				
Statistical Analysis Plan	n Pre-specified statistical methodology documented for the trial, either in the protocol or in a separate document.				

#### Introduction

This document is the Statistical Analysis Plan (SAP) for the GEM3 trial and should be read in conjunction with the current trial protocol. This SAP details the proposed analyses and presentation of the data for the main paper(s) reporting the results for the GEM3 trial.

The results reported in these papers will follow the strategy set out here. Subsequent analyses of a more exploratory nature will not be bound by this strategy, though they are expected to follow the broad principles laid down here. The principles are not intended to curtail exploratory analysis (e.g. to decide cut-points for categorisation of continuous variables), nor to prohibit accepted practices (e.g. transformation of data prior to analysis), but they are intended to establish rules that will be followed, as closely as possible, when analysing and reporting data.

Any deviations from this SAP will be described and justified in the final report or publication of the trial (using a table as shown in Appendix A). The analysis will be carried out by an appropriately qualified statistician, who should ensure integrity of the data during their data cleaning processes.

**Background and rationale** 

The background and rationale for the trial are outlined in detail in the protocol. In brief, GEM3 is a multi-centre, double-blind, randomised controlled trial (RCT) comparing the use of a combination of oral gefitinib and intramuscular methotrexate (MTX) against MTX and placebo as a non-surgical treatment to treat tubal ectopic pregnancy (EP).

#### Trial objectives

The primary objective is to test the hypothesis that administering gefitinib in combination with MTX reduces the rate of surgical intervention ('rescue surgery') for the treatment of tubal EP when compared with MTX alone.

Secondary objectives are as follows:

To assess the effects of a combination of MTX and gefitinib compared with MTX treatment alone, on:

The need for additional treatment with MTX.

The number of days to resolution of the pregnancy (resolution defined as serum human chorionic gonadotropin (hCG)  $\leq$  15 IU/L).

The number of hospital visits associated with treatment until resolution or scheduled/emergency 'rescue' surgery for EP.

To assess the safety and tolerability of combination MTX and gefitinib compared with MTX treatment alone.

#### **Trial methods**

#### Trial design

GEM3 is a multi-centre, prospective, double-blind, superiority, parallel group, phase III placebocontrolled randomised trial. Participants will be recruited in the United Kingdom (UK). Participants will be randomised to MTX and gefitinib or MTX and placebo. See trial schema in Appendix B.

Trial interventions

The intervention group will be given a single-dose intramuscular MTX (50 mg/m^2) injection (standard care) with seven daily doses of oral gefitinib (250 mg). The control group will be given a single-dose intramuscular MTX (50 mg/m^2) injection with seven daily doses of placebo (matched to the oral gefitinib tablet).

Primary outcome measure

The primary outcome is surgical intervention for the treatment of EP (salpingectomy or salpingostomy by laparoscopy or laparotomy).

Secondary outcome measures

Secondary outcomes are as follows:

Use of additional MTX (as directed by standardised expected change in serum hCG level).

Time to hCG resolution (days) from randomisation until hCG levels  $\leq$ 15IU/L.

Number of hospital visits associated with treatment until resolution or scheduled/emergency surgery.

Safety/tolerability (adverse events (AE)).

Acceptability of treatment (assessed 3 months after resolution of EP by Likert score).

Return to menses (assessed 3 months after resolution of EP).

Timing of outcome assessments

The schedule of trial procedures and outcome assessments are given in Appendix C.

Randomisation

Participants will be randomised in a 1:1 ratio to either MTX and gefitinib or MTX and placebo.

Randomisation will be provided by a secure online randomisation system at the Birmingham Clinical Trials Unit (BCTU) using a minimisation algorithm incorporating the following factors:

```
Baseline serum hCG levels (<1500 IU/L, \geq1500 to <2500 IU/L, \geq2500 IU/L)
Body Mass Index (BMI) (<25 kg/m^2, \geq25 kg/m^2)
Ectopic size on ultrasound (<2cm, \geq2cm)
Centre
```

A 'random element' will be included in the minimisation algorithm, so that each participant has a probability (unspecified here), of being randomised to the opposite intervention that they would have otherwise received. Full details of the algorithm used will be stored in a confidential document at BCTU.

#### Sample size

The target sample size of 328 participants is based on data taken from the Phase II study (GEM2), published cohort data [1] and an audit of Edinburgh and Imperial of women undergoing usual care (2012; focusing on those participants with serum hCG >1000 IU/L). The cohort and audit data suggest a 30% rate of surgical intervention in the MTX group, with 15% expected in the MTX and gefitinib group (actual figure from the phase II study was 14% but this has been conservatively rounded up). To detect this absolute difference in proportions of 15% with 90% power and an alpha error rate of 5%, a total of 322 participants would need to be randomised (161 per group). Assuming and adjusting for a 2% loss to follow-up rate, 328 participants need to be recruited.

#### Framework

The objective of the trial is to test the superiority of one intervention to another. The null hypothesis is that there is no difference in surgery rates between women allocated to MTX and gefitinib vs. women allocated to MTX and placebo. The alternative hypothesis is that there is a difference between the groups.

Interim analyses and stopping guidance

If gefitinib in combination with MTX is overwhelmingly better or worse than MTX alone with respect to reducing the rate of surgical intervention for resolution of EP, then this effect may become apparent before the target recruitment has been reached. Alternatively, new evidence could emerge from other sources to suggest that gefitinib in combination with MTX is definitely more, or less, effective than MTX alone. To protect against any unnecessary continuance of the

trial in this event, interim analyses of major endpoints and safety data will be supplied during the period of recruitment to the study, in strict confidence, to the Data Monitoring Committee (DMC) along with updates on results of other related studies, and any other analyses that the DMC may request.

The DMC will advise the chair of the Trial Steering Committee (TSC) if, in their view, any of the randomised comparisons in the trial have provided both: a) proof beyond reasonable doubt that for all, or for some, types of participant one particular intervention is definitely indicated or definitely contra-indicated in terms of a net difference of a major endpoint, and b) evidence that might reasonably be expected to influence the patient management of many clinicians who are already aware of the other main trial results. Unless this happens, however, the TSC, the collaborators and all of the central Trial staff (except the statisticians who supply the confidential analyses) will remain ignorant of the interim results.

Appropriate criteria of proof beyond reasonable doubt cannot be specified precisely, but a difference of at least p<0.001 (similar to a Haybittle-Peto [2] stopping boundary) in an interim analysis of a major endpoint may be required to justify halting, or modifying, the study prematurely. If this criterion were to be adopted, it would have the practical advantage that the exact number of interim analyses would be of little importance, so no fixed schedule is proposed. Given the proposed use of the Haybittle-Peto boundary no adjustment for multiple testing (to control the overall type I error rate) is proposed, i.e. the threshold for statistical significance at final analysis will still be p=0.05.

A separate DMC reporting template will be drafted and agreed by the DMC including an agreement on which outcomes will be reported at interim analyses. The statistical methods stated in this SAP will be followed for the agreed outcomes.

Timing of final analysis

The final analysis for the trial will occur after all participants have completed primary and secondary outcomes (where these are expected) and the corresponding outcome data has been entered onto the trial database and validated as being ready for analysis. This is provided that the trial has not been stopped early for any reason (e.g. TSC/DMC advice or funding body request).

Timing of other analyses

Further analysis will occur at 12 months post-randomisation on long-term follow-up data on future pregnancies and fertility. This analysis will subject to a separate SAP.

Trial comparisons

All references in this document to 'group' refer to MTX and gefitinib or MTX and placebo.

#### Statistical Principles

Confidence intervals and p-values

All estimates of differences between groups will be presented with two-sided 95% confidence intervals, unless otherwise stated. For the primary outcome (ITT, sensitivity/supportive and subgroup analyses), a p-value will be produced, with statistical significance considered at the 5% level.

Adjustments for multiplicity

No correction for multiple testing will be made.

Analysis populations

All primary analyses (primary and secondary outcomes including safety outcomes) will be by intention-to-treat (ITT). Participants will be analysed in the intervention group to which they were randomised, and all participants shall be included whether or not they received the allocated intervention. This is to avoid any potential bias in the analysis [3]. However, in rare instances where a participant is randomised and is later found to violate the inclusion criteria because no consent was collected (as randomised in error), they will be withdrawn and removed from any statistical analyses. Refer to section 5.4 for definition of adherence and definition of the per-protocol population and section 9.10 for further details on such sensitivity/supportive analyses.

Definition of adherence

Adherence to the allocated intervention (gefitinib/placebo) will be monitored by the participant's self-reported account of whether they took their allocated treatment, including total number of tablets taken. This data will be collected and recorded at each study visit. Adherence to MTX will be reported by the clinician on whether the initial methotrexate injection was given. We will define adherence as those participants who receive their initial methotrexate injection and took at least 75% of their allocated treatment prior to resolution (up to a maximum of seven daily doses if resolution not occurred by seven days post-randomisation). Any women who do not receive an initial MTX injection or their allocated intervention as a result of a clinical change in condition (clinical change requiring immediate surgery post-randomisation) will be considered adherent (it is anticipated that this is equally likely to occur in both the MTX and gefitinib and MTX and placebo

groups). Those women who are considered adherent will form the per-protocol (adherent) population.

#### Handing protocol deviations and violations

A protocol deviation/violation is defined as a failure to adhere to the protocol such as errors in applying the inclusion/exclusion criteria, the incorrect intervention being given, incorrect data being collected or measured or missed follow-up visits. We will include all participants in the primary analysis as per the ITT population described in section 5.3, regardless of deviation from the protocol, unless stated as a planned post-randomisation exclusion in section 5.3 [3]. This includes participants who were randomised but later found to violate the inclusion or exclusion criteria, however the outcomes in these women will be explored in a sensitivity analysis (see section 9.10). This does not include those participants who were randomised (and consented) and went on to withdraw consent post-randomisation for the use of their data. However, these women will be explored as per other missing responses.

#### Unblinding

For double-blind studies, the unblinding of the Trial Statistician to the intervention code will take place once the database is locked for final analysis unless the DMC request that they review the interim data with knowledge of the intervention groups or the DMC request to be unblinded at an interim analysis.

#### **Trial population**

#### Recruitment

A flow diagram (as recommended by Consolidated Standards of Reporting Trials (CONSORT) [4]) will be produced to describe the participant flow through each stage of the trial. This will include information on the number (with reasons) of losses to follow-up (drop-outs and withdrawals) over the course of the trial. A template for reporting this is provided in section 3 of the supplementary analysis report.

#### **Baseline characteristics**

The trial population will be tabulated as per section 6 of the supplementary analysis report. Categorical data will be summarised by number of participants, counts and percentages. Continuous data will be summarised by the number of participants, mean and standard deviation if deemed to be normally distributed or number of participants, median and interquartile range if data appear skewed, and ranges if appropriate. Tests of statistical significance will not be undertaken, nor confidence intervals presented [5]. Intervention

Description of the intervention

A template for reporting information on the intervention is provided in section 7 of the supplementary analysis report.

Adherence to allocated intervention

A cross-tabulation of allocated intervention by the adherence categories stated in section 5.4 will be produced (proportions and percentages). A template for reporting adherence is provided in section 7 of the supplementary analysis report.

#### **Protocol deviations**

Frequencies and percentages by group will be tabulated for the protocol deviations and violations as per section 5 of the supplementary analysis report.

#### **Analysis methods**

Intervention groups will be compared using regression models to adjust for all covariates as specified in section 9.1 where possible.

#### Covariate adjustment

In the first instance, intervention effects between groups for all outcomes will be adjusted for the minimisation parameters listed in section 4.6. Centre will be included with a random intercept in the model, and all other factors as fixed effects (with the exception of time to event outcomes where centre will be regarded as a fixed effect).

If covariate adjustment is not possible (e.g. the model does not converge), randomising centre will be removed first. If this reduced model still fails to converge, unadjusted estimates will be produced and it will be made clear in the final report why this occurred (e.g. not possible due to low event rate/lack of model convergence).

For binary outcomes only, if the (full) adjusted log-binomial model fails to converge (when estimating a risk ratio); a Poisson regression model with robust standard errors will be used to estimate the same parameters [6]. If this also fails to converge, estimates will be produced from the log-binomial model (following rules for removal of variables as outlined above). It will be made clear in the final report why this occurred (e.g. not possible due to low event rate/lack of model convergence).

#### Distributional checks

There are no continuous outcome measures proposed in the GEM3 trial.

For time to event outcomes (analysed using a cox regression model), the proportional hazard assumption will be assess visually using log cumulative hazard versus log time plots. If these plots identify potential non-proportional hazards, time-varying covariates will be considered.

#### Handling missing data

In the first instance, analysis will be completed on received data only with every effort made to follow-up participants even after protocol violation to minimise any potential for bias. To examine the possible impact of missing data on the results, and to make sure we are complying with the ITT principle, sensitivity analyses will be performed on the primary outcome measure (surgical intervention) [7]. See section 9.10 for further details.

Data manipulations

See Appendix D.

Analysis methods – primary outcome

A template for reporting the primary outcome is given in section 8.1 of the supplementary analysis report. The primary outcome will be summarised using frequencies and percentages. A mixed effects log-binomial model will be used to generate an adjusted risk ratios (RR) (and 95% CIs). Adjusted risk differences (RD) (and 95% CIs) will also be presented (using an identity link function). Statistical significance of the treatment group parameter will be determined (p-value generated) through examination of the associated chi-squared statistic (this will be obtained from the model which produces the RR). See section 9.1 for covariate adjustment and model convergence.

Analysis methods – secondary outcomes

A template for reporting the secondary outcomes is given in section 8.2 of the supplementary analysis report. See section 9.1 for covariate adjustment and model convergence.

Time to hCG resolution will be considered in a competing risk framework [8]. This is to account for participants who have surgical intervention for their EP, which interferes with the natural path of hCG levels and hence hCG resolution (≤15 IU/L). A cumulative incidence function will be used to estimate the probability of occurrence (hCG resolution) over time. This method is favoured over Kaplan-Meier methods which may overestimate this probability. A Fine-Gray model will be used to estimate subdistribution adjusted hazard ratios (and 95% CIs) directly from the cumulative incidence function. In addition, a further Cox Proportional Hazard model will be fitted and applied to the cause-specific (non-surgical resolution) hazard function and used to generate

adjusted hazard ratios (and 95% CIs) (effectively censoring surgical events at the point of surgery) [9].

Time to event data (return to menses) will be summarised using medians and interquartile ranges. A Cox Proportional Hazard model will be fitted to generate an adjusted hazard ratio (and 95% CI) and a Kaplan Meier plot will be produced to assess the data visually.

Binary outcomes (additional MTX, adverse events) will be analysed as per the primary outcome.

Categorical outcomes of an ordinal nature (acceptability of treatment measured using a Likert scale) will be summarised using frequencies and percentages. An ordinal logistic regression model will be used to generate adjusted odds ratios (and 95% CIs).

For secondary outcome measures which measure counts (number of hospital visits associated with treatment until resolution or scheduled/emergency surgery), this data will be summarised using medians with interquartile ranges. If appropriate, a Poisson model will be used to generate incidence rate ratios (and 95% CIs). An offset term will be included in each model to account for length of exposure time (see data manipulations (Appendix D) for how this will be derived). A negative binomial regression model may be considered if the data are overdispersed.

Analysis methods – exploratory outcomes and analyses

Any data that does not form a pre-specified outcome will be presented using simple summary statistics by intervention group (i.e. numbers and percentages for binary data and means (or medians) and standard deviations (or inter-quartile ranges) for continuous normal (or non-normal) data).

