If 'Have you had any extra visits to hospital related to this EP'=yes then number of additional visits should be provided.

If a woman does not have a post-treatment visit as a result of immediate surgery following randomisation we will assume number of extra visits=0.

Where a woman has X post-treatment visits, sum the total number of extra visits (A) as follows:

A=(Number of extra visits at visit 1 + Number of extra visits at visit 2 + ... + Number of extra visits at visit X)

Secondly, we look at the number of hospital attendances:

Remove any post-treatment visits where a woman did not have a hospital visit (hCG measurement/USS scan/additional MTX used as a proxy for hospital attendance i.e. if none of these are performed we can assume the visit was conducted remotely). Count the number of post-treatment visits with hospital attendance (X). The number of hospital attendances (B) can be calculated as follows:

If a woman had surgery and this occurred on a different day to a post-treatment visit then

B=X+1

If a woman did not have surgery or surgery occurred on the same day as a post-treatment visit then

B=X

Finally, the total number of hospital visits associated with treatment can then be calculated as follows:

Total number of hospital visits associated with treatment=A+B

Length of follow-up (in days) for the offset term for the Poisson model will be calculated as:

Date of resolution\*-Date of randomisation

\*Date of resolution is date of surgery (salpingectomy or salpingostomy/salpingostomy) or earliest date post-randomisation where hCG level is  $\leq$ 15 IU/L. If a date of resolution is missing (no surgery and not followed up to a hCG  $\leq$ 15 IU/L) and site have confirmed woman's pregnancy has resolved and no surgery performed, date of most recent hCG measurement will be used as date of resolution.

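### The hospital-visit model is offset by days to resolution or surgery, so it estimates visits per day, whereas the objective names the number of visits

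*SAP*

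**What the plan says.** Section 3 (Trial objectives) asks for the effect on "The number of hospital visits associated with treatment until resolution or scheduled/emergency 'rescue' surgery for EP". Section 4.4 lists the matching outcome: "Number of hospital visits associated with treatment until resolution or scheduled/emergency surgery". Both describe a total per woman, and neither mentions a rate. Section 3 also has a separate objective on "The number of days to resolution of the pregnancy".

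Section 9.6 summarises the count by medians and interquartile ranges. It then says "If appropriate, a Poisson model will be used to generate incidence rate ratios (and 95% CIs", followed by "An offset term will be included in each model to account for length of exposure time". A negative binomial model may replace the Poisson model if the data are overdispersed.

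Appendix D counts extra visits (A) plus hospital attendances (B) and discards visits after resolution, where resolution means surgery or hCG ≤15 IU/L. It then defines the offset: "Length of follow-up (in days) for the offset term for the Poisson model will be calculated as" "Date of resolution\*-Date of randomisation". The date of resolution is the date of surgery or of the first hCG ≤15 IU/L. If neither is available but the site confirms resolution without surgery, the date of the last hCG measurement is used.

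**The concern.** An offset is the right tool when women are observed for different lengths of time for reasons unrelated to the effect of treatment. Here, for most women, the exposure time is simply the time taken to reach the event that ends the count. That time arises after randomisation and can be changed by gefitinib. It is also built from the same dates as the time-to-resolution outcome and the surgery outcome.

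Dividing by it removes the most direct way in which treatment could reduce the visit burden, which is to bring the episode to an end sooner. The model-based ratio is the only between-group estimate planned for this objective. If it estimates something else, the objective is left with two unadjusted medians and no contrast or confidence interval.

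**Working it through.** **Inputs.** From the SAP: surgery rates of 30% (MTX and placebo) and 15% (MTX and gefitinib), section 4.7. The SAP gives no figure for visits, visit frequency or time to resolution, so there is no stated result to reproduce for this outcome. All visit patterns and durations below are assumptions.

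**What the model estimates.** Let V be visits and T days to resolution or surgery. For a Poisson model with log link, offset log(T) and treatment as the only term,

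IRR = (ΣV₁/ΣT₁)/(ΣV₀/ΣT₀) = (ratio of mean visits)/(ratio of mean days).

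Without the offset the same model gives the ratio of mean visits. The two agree only when mean days are equal between groups. Covariate adjustment or a negative binomial form changes the exact estimate, but the quantity is still visits per day.

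**Check 1: faster resolution, constant visit frequency.** If mean days fall by 25%, mean visits fall by 25%. The count ratio is 0.75 and the offset ratio is 0.75/0.75 = 1.00. A simulation with 200,000 women per arm, one visit per week on average, no surgery and mean times of 28 days (placebo) and 21 days (gefitinib) gave mean visits of 4.00 and 3.01. The count ratio was 0.75 and the offset ratio 1.00.

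**Check 2: the SAP's surgery rates, with assumed patterns for operated and other women.** Each arm mean is s × (operated) + (1 − s) × (not operated), with s = 0.15 for gefitinib and 0.30 for placebo. For 3 visits in 7 days (operated) and 6 visits in 30 days (others):

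- Visits: gefitinib 0.15×3 + 0.85×6 = 5.55; placebo 0.30×3 + 0.70×6 = 5.10; ratio 1.09.
- Days: gefitinib 0.15×7 + 0.85×30 = 26.55; placebo 0.30×7 + 0.70×30 = 23.10.
- Offset ratio: (5.55/26.55)/(5.10/23.10) = 0.95.

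Varying the assumptions:

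| Operated | Not operated | Count ratio | Offset ratio |
|---|---|---|---|
| 3 visits/7 days | 6/30 | 1.09 | 0.95 |
| 2/4 | 7/35 | 1.14 | 0.96 |
| 4/10 | 6/28 | 1.06 | 0.94 |
| 3/15 | 6/30 | 1.09 | 1.00 |
| 3/18 | 6/30 | 1.09 | 1.02 |

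The direction reverses in the first three rows, where operated women have clearly more visits per day than the others. At an equal daily rate (3/15 and 6/30) the offset ratio is exactly 1.00. At a lower daily rate (3/18) the direction is kept.

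**Check 3: visits concentrated early.** A simulation assumed visits on days 4 and 7 and then weekly, one further visit for surgery, surgery at about day 10 and the SAP's surgery rates. With non-surgical times of 28 days (placebo) and 21 days (gefitinib), mean visits were 4.80 and 4.24: count ratio 0.88, offset ratio 1.03. With 28 days in both arms they were 4.79 and 5.10: count ratio 1.06, offset ratio 0.95. The offset can therefore mislead either way.

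**Zero time.** Surgery on the day of randomisation gives an offset of log(0). Appendix D adds 0.01 days to a zero time to surgery in the hCG analysis, but does not repeat this for the visit offset.

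**The case against.** Several points on the other side have force.

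- *Observation time is not wholly uniform.* A reader might infer that every woman is counted to the same end point, so that an exposure term has no purpose at all. The SAP does not support that. Its amendment table records that some sites do not follow women to hCG ≤15 IU/L as standard care, and Appendix D closes the window at the last hCG measurement for site-confirmed resolutions. Some counts do stop short. This stands, but it does not justify applying the offset to every woman, most of whose durations are themselves outcomes.
- *Lost women.* A reader might also blame the offset for losing women with neither a resolution date nor site confirmation. That is not a separate fault. Section 9.3 analyses received data only, and those women's counts would be incomplete without the offset too.
- *Zero time.* For operated women the offset equals the time to surgery that Appendix D already corrects. The omission is a drafting gap that a cross-reference closes.
- *The count has its own difficulty.* Early surgery ends the count. In Check 2 the ratio of 1.09 goes against gefitinib only because fewer women have their episode cut short by surgery. The count ratio matches the stated objective, but it is not a pure measure of benefit.
- *Limited consequence.* This is one of six secondary outcomes. Section 5.1 plans p-values for the primary outcome, the output is openly called an incidence rate ratio, and medians of the count remain visible.

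The wording "If appropriate, a Poisson model will be used to generate incidence rate ratios (and 95% CIs" does not rescue the plan. The condition governs whether the Poisson model is used, while the offset goes into each model. Medians with interquartile ranges supply no adjusted contrast and no confidence interval.

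**Conclusion.** Wrong as written; should-fix. The model in section 9.6, with the offset in Appendix D, estimates visits per day and so does not answer the objective in section 3 or the outcome in section 4.4. This follows from the structure of the model and needs no assumed figures.

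The size does need assumptions. A 25% reduction in visits that comes entirely from 25% faster resolution would be reported as no effect. Under the SAP's surgery rates, a count ratio of 1.09 can appear as anything from 0.95 to 1.02 across the patterns tried with 6 visits in 30 days for women not operated on. A reader might infer that the offset will reverse the direction. The documents do not support that: the SAP gives no visit rates or durations, its objective for days to resolution is only to assess the effect, and some plausible patterns show no reversal. The supported statement is that the offset can cancel or reverse the contrast. The primary conclusion is unaffected.

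**What to change.** 1. In section 9.6 and Appendix D, make the main model the total count (A+B) to resolution or surgery without an offset. Use a negative binomial model, or Poisson with robust standard errors, adjusted as in section 9.1, and report the ratio of mean visits with 95% CI.
2. If a per-day rate is still wanted, keep it as supplementary output labelled as a rate, and apply the 0.01-day zero-time rule from the hCG derivation to its offset.
3. Treat women with no resolution date and no site confirmation as missing. Add a sensitivity analysis that excludes site-confirmed resolutions counted only to the last hCG measurement.
4. State that a lower count can also reflect earlier surgery, so the ratio is to be read alongside the surgery rates.

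The cost is a change of SAP wording and one short sensitivity analysis. No new data are needed and the main model becomes simpler.
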